1.4 Primary Objectives

The primary objective is to assess the effectiveness of tPCS in improving total sleep time by 20% in children with neurodevelopmental disorder, compared with using Melatonin.

1.5 Secondary Objectives

The secondary objective is to evaluate improvement in other objective sleep measures such as sleep onset latency, sleep efficiency, and wake after sleep onset based on actigraphy; and subjective sleep measures such as sleep initiation, sleep maintenance, sleep quality and change in behaviour based on questionnaires in children with neurodevelopmental disorder.

We also hypothesise that objective improvement in sleep quality will correlate with a decreased score in Sleep Disturbance Scale in Children questionnaire.

1.6 Potential Risks and Benefits:

1.6.1 Potential Risks

tPCS may cause discomfort or tingling sensation to some people. Some people may have skin redness due to allergic reaction to electrode. Few people may complain of headache post stimulation. Otherwise, there is minimal risk in tPCS if there are no contraindication.

1.6.2 Potential Benefits

Use of tPCS is potentially an effective intervention for children with neurodevelopmental disorder that can improve spasticity, motor function and sleep.

2 STUDY POPULATION

2.1 List Number and Nature of Subjects to be enrolled

[figure not shown]
Based on a two-sided paired t-test at 80% power and 5% one-sided alpha with 20% drop-out rate, a sample size of 40 is required to detect 20% improvement in primary end-point (total sleep time), assuming 15% standard deviation.

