3 STUDY DESIGN

Figure C: Study Design

At baseline (week 0), all patients will do a one-week sleep actigraphy and complete SDSC questionnaire. At week 1, patients will be randomised to one of the 4 treatment regimen that is determined by the first period of the sequence they are assigned to. Re-evaluation with sleep actigraphy and SDSC questionnaire will be done at week 4, 6 and 10. At week 7, the patients will cross over to the treatment for the second period of the sequence they are assigned to. Over the 10-week period, sleep diary will also be completed daily.

10 patients will receive dose-appropriate Melatonin over 8 weeks (Group A), 10 patients will receive 40 sessions of home-based tPCS over 8 weeks (Group D), 10 patients will receive 4 weeks of Melatonin then cross over to receive 4 weeks of 20 sessions of home-based tPCS (Group B) and 10 patients will receive 4 weeks of 20 sessions of home-based tPCS then cross over to receive Melatonin over 4 weeks (Group C).

There will be a washout period of 2 weeks (week 5 and 6) between cross over. Those on a Melatonin group cross over will also go through the same washout period.

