8 SAMPLE SIZE AND STATISTICAL METHODS

8.1 Determination of Sample Size

In an inequality test on data from the Balaam's crossover design, a sample size of 32 achieves 83% power at a 5% significance level when the absolute difference between the two treatment means is 0.2 and the within-subject standard deviation is 0.15. To account for 20% drop-out rate, a sample size of 40 (10 in each arm) is required.

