8.2 Statistical and Analytical Plans

The SPSS® 25.0 software (IBM, Armonk, New York, United States) will be used, with statistical significance defined as a p-value of <0.05 . Independent t-tests will be conducted to compare differences in outcomes between the two treatment groups; Wilcoxon signed-rank test will be used to compare continuous variables at start and end of treatment. Average of actigraphic measurements were used to compare effects of treatment on sleep parameters. One-way Repeated Measure ANOVA will be conducted to assess changes in outcomes and patient scores within the group across the timepoints. Non-parametric testing will also be conducted to observe for significant differences in patient outcomes within the groups at each timepoint.

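### Section 2.1 credits the 40 children to a paired t-test that gives 8 to 14 and is called both two-sided and one-sided; the 40 comes from the Balaam calculation in 8.1, whose 83% power fits only a one-sided 5% test

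*Protocol*

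**What the plan says.** The protocol justifies the sample size twice.

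- **Section 2.1** opens with "Based on a two-sided paired t-test at 80% power and 5% one-sided alpha with 20% drop-out rate" and concludes that "a sample size of 40 is required to detect 20% improvement in primary end-point (total sleep time), assuming 15% standard deviation". It does not say whether the 15% is the SD of a single measurement or of the within-child difference.
- **Section 8.1** uses a Balaam crossover calculation and reports that "a sample size of 32 achieves 83% power at a 5% significance level". The inputs behind that figure are given as follows: "the absolute difference between the two treatment means is 0.2 and the within-subject standard deviation is 0.15". The section then allows for 20% drop-out to reach 40, that is, 10 per arm. It does not state whether the 5% is one-sided or two-sided.

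Three other places bear on this.

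- **Section 1.4** gives the primary contrast as "improving total sleep time by 20% in children with neurodevelopmental disorder, compared with using Melatonin".
- **Section 3** assigns four groups. Of these, "10 patients will receive dose-appropriate Melatonin over 8 weeks (Group A)" and Group D receives tPCS in both periods. Only Groups B and C switch treatment.
- **Section 8.2** has "statistical significance defined as a p-value of <0.05", again with no sidedness.

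**The concern.** Two different tests (paired t-test and Balaam contrast), two powers (80% and 83%) and two descriptions of the SD are offered for one sample size. They cannot both be its source. Within 2.1, one sentence calls the test two-sided and the alpha one-sided.

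A paired t-test also does not fit the primary contrast. A child in Group A or D has no tPCS-versus-Melatonin pair, so half the children could not contribute to it.

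What is at stake is the power that the trial can claim. If sidedness is settled one way, the planned evaluable sample exceeds the 80% named in 2.1. If it is settled the other way, the sample falls short.

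**Working it through.** **Inputs.** Difference δ = 0.20, SD 0.15, α = 5%, drop-out 20% (2.1 and 8.1). Power target 80% (2.1). 32 evaluable children, 8 in each of four sequences, for 83% power (8.1). Power is taken from the noncentral t distribution throughout.

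**1. The plan's own figure, from 8.1.** Section 1.2.4 justifies the design because its treatment estimate stays unbiased under unequal carryover. That describes the carryover-adjusted contrast. With d the period 2 minus period 1 difference and n children per sequence:

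- Estimate = [(d_B − d_A) + (d_D − d_C)] / 2
- Each mean difference has variance 2σ_w²/n, so the estimate has variance (1/4) × 4 × 2σ_w²/n = 2σ_w²/n
- SE = 0.15 × √(2/8) = 0.075
- Noncentrality = 0.20 / 0.075 = 2.667, df = 4n − 4 = 28

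| Evaluable (per sequence) | One-sided 5% | Two-sided 5% |
|---|---|---|
| 28 (7) | 78.2% | 66.8% |
| 32 (8) | **83.1%** | **73.0%** |
| 36 (9) | 86.9% | 78.3% |
| 40 (10) | 90.0% | 82.7% |

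Using df = 29 changes the two-sided figure for 32 children only to 73.2%. So 32 children at 83% is reproduced one-sided and not two-sided. It is also the smallest balanced total that reaches 80% one-sided. The drop-out step is right: 32 / 0.8 = 40.

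**2. Could another estimator explain 83%?** Using only Groups B and C with no carryover adjustment, the variance is σ_w²/n, SE = 0.15 × √(1/8) = 0.053 and noncentrality = 3.771. With df between 14 and 29, power is 94% to 95% two-sided and 97% to 98% one-sided. This does not give 83%.

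**3. The paired t-test named in 2.1.** Noncentrality = (δ / SD_diff) × √n, df = n − 1, target 80%; enrolled = n / 0.8, rounded up.

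| Meaning of 15% | SD_diff | δ / SD_diff | Sides | Evaluable n (power) | Enrolled |
|---|---|---|---|---|---|
| SD of the difference | 0.150 | 1.333 | one | 6 (87.4%) | 8 |
| SD of the difference | 0.150 | 1.333 | two | 7 (83.4%) | 9 |
| Within-subject SD, as in 8.1 | 0.15 × √2 = 0.212 | 0.943 | one | 9 (82.5%) | 12 |
| Within-subject SD, as in 8.1 | 0.212 | 0.943 | two | 11 (80.4%) | 14 |

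In each row one child fewer falls below 80%: 78.7%, 74.3%, 77.4% and 75.6%. With 32 pairs, power would exceed 99.9% on every row. For the test to need 32 pairs at 80% power, SD_diff would have to be about 0.39 (two-sided) or 0.44 (one-sided), against 0.15 or 0.212.

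**4. Other readings of 2.1.**

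- Only Groups B and C supply pairs, so the trial total is doubled: 16, 18, 24 or 28 enrolled.
- A separate paired test in each of four groups: 32, 36, 48 or 56 enrolled.

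None gives 40.

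**The case against.** Five points can be made for the plan.

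- **The range 8 to 14 is only one reading.** If only the children who switch supply pairs, the total is 16 to 28, and a per-group reading gives 32 to 56, which brackets 40. This stands as a caution on the range. No reading yields 40, so the conclusion is unaffected.
- **The 83% might be two-sided after all.** The same contrast gives 82.7% two-sided with 40 evaluable children, which rounds to 83%, and 8.1 speaks of an inequality test and an absolute difference, which lean towards a non-directional test. The arithmetic is right, so how the figure arose cannot be proved. But 8.1 attaches 83% to 32 and then adds children for drop-out, and 2.5 says that drop-outs are not replaced. As written, the figure for 32 fits one-sided only. Attaching it to 40 would mean that no drop-out allowance had been made.
- **The estimator is an assumption.** 8.1 does not name it, and 8.2 lists independent t-tests, Wilcoxon signed-rank tests and repeated-measures ANOVA instead. This stands as a limit: 83% and 73% are powers of the contrast behind 8.1, not of the tests in 8.2. The assumption is supported by 1.2.4 and by its agreement with the stated 83%.
- **Sidedness and scale can be left to a SAP.** This is fair for 8.2 taken alone. It does not excuse a protocol sentence that states two sidednesses, or a sample size credited to a test that does not produce it.
- **The practical effect is small.** Enrolment of 40 need not change, and the paired test of 2.1 would be overpowered at 32. That is true of the number enrolled. It is not true of the power claimed, which remains undetermined.

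**Conclusion.** The concern holds. Section 2.1 is wrong as written: the named paired t-test gives 8 to 14 enrolled on its direct reading and 40 on none of the readings tried, and the sentence contradicts itself on sidedness. The 40 is the result of 8.1.

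Under the carryover-adjusted Balaam contrast, with a difference of 0.2 and a within-subject SD of 0.15, the 32 evaluable children have 83% power at one-sided 5% and about 73% at two-sided 5%. The gap of about 10 percentage points straddles the 80% target of 2.1, and nothing in 8.1 or 8.2 settles which figure applies. The paired t-test finding does not depend on the Balaam estimator; the 83% and 73% figures do.

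**What to change.** 1. In 2.1, delete the paired t-test sentence and refer to 8.1 for the basis of the 40.
2. In 8.1, name the contrast, state one sidedness, and give the power that belongs to it for 32 evaluable children: 83% if one-sided 5%, about 73% if two-sided 5%. The choice should follow from the hypothesis, not from which figure is to be kept.
3. In 8.1, state that 0.15 is the within-subject SD and on which scale, for example as a proportion of baseline total sleep time.
4. In 8.2, give the p-value threshold the same sidedness.

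**Cost.** A text amendment to 2.1, 8.1 and one clause of 8.2; enrolment stays at 40. If the sponsor chooses a two-sided test and wants at least 80% power, 36 evaluable children fall short (78.3%) and 40 suffice (82.7%), which means 40 / 0.8 = 50 enrolled. The travel allowance in section 14 is costed for 40 subjects, so the budget would have to be revised. Otherwise the protocol should accept and state about 73%.

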2.2 Criteria for Recruitment and Recruitment Process

The eligible participants will be recruited from the families who receive services and/or medical follow-up at KKH. Information of the study and Consent Form will be provided to the families who show interest in the study.

2.3 Inclusion Criteria

- Aged 4-16
- Neurodevelopmental disorder including cerebral palsy, autistic spectrum disorder, neurogenetic syndrome.
- Patients whose pre-intervention sleep questionnaire total score more than 46 and/or pre-intervention sleep questionnaire T-score more than 70 in any sleep domain
- Children agree to tPCS as per procedure and consent to the study, including need to shave hair at the site of stimulation at the occiput (refer Figure B)
- Parents/carers agree to bring children to KKH for tPCS as per visit schedule and procedure
- Medical practitioner's approval

2.4 On Exclusion Criteria

History of uncontrolled epileptic disorders and seizures, brain tumours or trauma and mental diseases, substance abuse or dependence, use of benzodiazepines, neuroleptic, serotonin or dopaminergic drugs, presence of metal/ electronic implant in brain/ body eg. shunt, cochlear implant, pacemaker or defibrillator, known untreated obstructive sleep apnoea or other sleep disorder, and current involvement in other tDCS or rTMS trials. Patients with history of drug allergy to Melatonin will also be excluded.

[figure not shown]
2.5 Subject Replacement

Drop-out definition: Any participant who reports significant adverse effects, are unable tolerate the session, or withdraw from the study will be considered drop-out.

Subjects who drop out will not be replaced.

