2.1 Sleep disturbance scale for children (SDSC) and Aberrant Behavior Checklist (ABC)

2.2 WHO International Classification of Functioning, Disability and Health, Children & Youth version (ICF-CY) sleep ratings

³Actigraphy. Participants will collect the Actiwatch and wear it for 1 week at home for whole night actigraphic data at start of the sequence period (Week 0 and Week 6) and at the end of the sequence period (Week 4 and Week 10). Patients will return the Actiwatch at the end of the study.

⁴Transcranial Pulsed Current Stimulation (tPCS) – for intervention arm. 45min/ session of tPCS will be performed at home, supervised by a trained personnel, Monday to Friday for 20 sessions over 4 weeks in each sequence period. Participants will be asked to fill out the compliance/ adverse event log daily.

⁵In the control group, participants will be given Melatonin over 4 weeks in each sequence period. They will be asked to fill out the compliance/ adverse event log daily.

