3.4 Discontinuation/Withdrawal

3.4.1 Discontinuation Criteria

Study intervention will be discontinued if subject is unable to tolerate the tPCS or Melatonin.

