3.4.2 Discontinuation Visit and Procedures

Subjects may withdraw voluntarily from participation in the study at any time. If withdrawal occurs, subjects will still be asked to complete a questionnaire to study the reason for withdrawal. Actigraphy will be done (if any) to the point of withdrawal from participation in the study.

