5.5 Blinding

Blinding is not done to the patients. Only the study member reporting the actigraphy, and the study member performing data analysis will be blinded.

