6.4 Safety Monitoring Plan

All data will be entered into a secure password-protected document in the desktop. Access to the data will only be open to the study investigators. Hardcopy of the data forms will be stored in a locked cupboard in the department.

All adverse events of tPCS in all participants will also be logged and safety of tPCS will be monitored by the principal investigator.

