6.5 Complaint Handling

If there is any complaint of the tPCS, the Principal Investigator will be informed immediately to rectify the issue. If the subject is unable to tolerate the tPCS, the study will be discontinued.

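### The protocol does not settle whether a child who cannot tolerate treatment stops treatment or leaves the study; if it means leaving, later total sleep time is lost for a treatment-related reason

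*Protocol*

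**What the plan says.** Four places in the protocol bear on a child who cannot tolerate treatment.

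- **Section 3.4.1, Discontinuation Criteria:** "Study intervention will be discontinued if subject is unable to tolerate the tPCS or Melatonin". It covers both treatments, and what stops is the intervention. Follow-up is not mentioned.
- **Section 6.5, Complaint Handling:** "If the subject is unable to tolerate the tPCS, the study will be discontinued". It names tPCS only, and what stops is the study.
- **Section 2.5, Subject Replacement:** "Any participant who reports significant adverse effects, are unable tolerate the session, or withdraw from the study will be considered drop-out". Such children are not replaced.
- **Section 3.4.2, Discontinuation Visit and Procedures:** this is written for voluntary withdrawal. It says "If withdrawal occurs, subjects will still be asked to complete a questionnaire to study the reason for withdrawal", and then "Actigraphy will be done (if any) to the point of withdrawal from participation in the study".

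The assessments are set out elsewhere. Section 3 schedules actigraphy and the sleep questionnaire at weeks 4, 6 and 10 after baseline, without a condition that the child is still on treatment. Section 3.3 (footnote 3 to the visit table) and Section 3.3.2 place post-treatment actigraphy in the last week of each period, that is, weeks 4 and 10. Total sleep time, the primary outcome in Section 1.4, comes from those recordings. On blinding, Section 5.5 says "Blinding is not done to the patients".

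**The concern.** Stopping a treatment and leaving a study are different events, and the protocol uses both for the same child. A site could follow Section 3.4.1 and keep the child on the assessment schedule, or follow Section 6.5 and end participation. No sentence says which applies.

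The choice decides whether the primary outcome exists for that child. Each period has one post-treatment recording week, at its end. A child treated as having left earlier in the period has nothing recorded there. The reason for the gap would be the child's response to a treatment that the family knows the child is receiving, so the gap would not be unrelated to treatment, and it could differ between tPCS and Melatonin. How missing values are analysed may properly be left to a statistical analysis plan that is not shown. Whether the recordings are made is fixed by the protocol, and no analysis can restore recordings that were never made.

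**Working it through.** **1. The sections side by side, for a child who cannot tolerate tPCS.**

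| Section | What happens | Melatonin covered? | Follow-up stated? |
|---|---|---|---|
| 3.4.1 | intervention stops | yes | no |
| 6.5 | study stops | no | no, but leaving is implied |
| 2.5 | counted as a drop-out | not named; refers to adverse effects or to tolerating the session | no |
| 3.4.2 | actigraphy ends at withdrawal | yes (any withdrawal) | yes, for voluntary withdrawal |

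The direct conflict is Section 3.4.1 against Section 6.5. One course satisfies every row: treatment stops, the child leaves, and is counted as a drop-out. Staying in follow-up also satisfies Section 3.4.1 and the Section 3 schedule. The text does not choose between them.

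**2. What is lost under each reading.**

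- *Stops treatment, stays in the study:* weeks 4, 6 and 10 remain on the schedule and nothing need be lost.
- *Leaves before the week 4 recording:* weeks 4, 6 and 10 are all missed, so there is no post-treatment total sleep time in either period.
- *Leaves in period 2 before the week 10 recording:* weeks 4 and 6 are kept and week 10 is missed.
- *Leaves during a recording week:* some nights may be kept, since Section 3.4.2 allows actigraphy up to the point of withdrawal.

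**3. The plan's own allowance.** Section 8.1 takes 32 evaluable children and a 20% drop-out rate: 32 / (1 − 0.20) = 40, which reproduces. With 8 per sequence, a within-subject SD of 0.15, a difference of 0.2 and 29 degrees of freedom, the stated 83% power also reproduces (83.1%) if the 5% level is one-sided. Two-sided it would be 73.2%, but sidedness is a separate matter.

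**4. What that allowance buys.** Let d be period 2 minus period 1 within a child. With the groups as in Section 3 (A Melatonin twice, B Melatonin then tPCS, C tPCS then Melatonin, D tPCS twice), the usual Balaam estimate is

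½ × [(d_B − d_A) + (d_D − d_C)], with variance 2 × SD² / n for n children per sequence.

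- n = 10: √(2 × 0.0225 / 10) = 0.067
- n = 8: √(2 × 0.0225 / 8) = 0.075

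The allowance protects the standard error at 8 per sequence. It does nothing about which children are missing.

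**5. Weight of one child.** Under this estimate, a child missing either post-treatment week contributes no d: 1/40 = 2.5% of the trial and 1/10 = 10% of the sequence. This is the weight of any lost child, whatever the cause; it does not measure this defect. Thirty children are due tPCS (B, C, D) and 30 are due Melatonin (A, B, C). The protocol gives no expected number who will stop for intolerance.

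**The case against.** The strongest reply is that this is loose wording rather than a flaw in design. Section 3.4.1 carries the heading for discontinuation, covers both treatments and stops only the intervention. Section 6.5 is one line about complaints over the device, which explains why it names tPCS alone. Section 2.5 sits under replacement and may only define who is counted. Section 3.4.2 concerns voluntary withdrawal and reaches intolerant children only by inference. On that view a child who stops treatment simply stays on the Section 3 schedule.

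Much of this stands, and it rules out several stronger readings. A reader might infer that the protocol requires intolerant children to leave; it does not, since that follows only from Section 6.5 taken literally. A reader might infer that Section 2.5 itself ends assessment; it says nothing about assessment. A reader might infer that losses will be heavier on tPCS; the tPCS-only wording makes that possible but does not show it.

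A reader might also infer that the tPCS effect will be overstated by a calculable amount. One can construct a figure: if 5% to 20% of children on tPCS left and would have gained nothing while the rest gained 0.20, the effect in all children would be 0.95 × 0.20 = 0.19 down to 0.80 × 0.20 = 0.16, so completers would overstate it by 0.01 to 0.04. Neither the rates nor the zero gain is in the documents, so this is not evidence of size or direction.

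Finally, the count in which a child's whole contribution is lost assumes the period-difference estimate. Section 8.2 names other tests, and a mixed model could still use a period 1 value.

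What the reply does not remove is that Sections 3.4.1 and 6.5 name different things to be stopped, and that no sentence keeps a child who stops treatment in follow-up.

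**Conclusion.** The point holds in a conditional form. Sections 3.4.1 and 6.5 conflict on what ends when a child cannot tolerate tPCS, and Section 2.5 leaves it open. If Section 6.5 is applied as leaving the study and the Section 3.4.2 cut-off is extended to such a child, post-treatment total sleep time is lost for that period, when the child leaves before its last week, and for any later period. The loss would be treatment-related in a trial with unblinded patients, and the 20% allowance covers precision only.

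The number of children affected may be small. The size and direction of any bias cannot be derived from the documents, and none is claimed. The conclusion rests on two assumptions: that some children will stop for intolerance, and that at least some sites would act on the wording of Section 6.5. The correction should be made because it is cheap and the data cannot be recovered afterwards; the point does not show the design to be unsound.

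**What to change.** Reconcile Sections 2.5, 3.4.1, 3.4.2 and 6.5.

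- Define *stopped study treatment* separately from *withdrew from follow-up*, in the same words for tPCS and Melatonin.
- State to which of the two the drop-out label in Section 2.5 and the actigraphy cut-off in Section 3.4.2 apply.
- State that a child who stops treatment but has not withdrawn is still asked to complete the already scheduled week 4, 6 and 10 actigraphy and questionnaires, where the family agrees.

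When treatment should stop, and whether period 2 treatment is given, are clinical matters for the sponsor; nothing is proposed on them here.

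The cost is protocol wording and a few off-treatment assessments at visits that already exist. Including children assessed off treatment may also make the estimated effect smaller than one based only on those who stayed on it. That is a possible consequence of the comparison chosen, and Sections 1.3 and 1.4 neither require nor exclude such a comparison.
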